9.7 Data Analyses

To examine the primary hypothesis that BB-12 supplementation will protect against antibiotic-induced SCFA reduction, the mixed model will be used to analyze the treatment effect on the antibiotic-induced SCFA reduction. Statistical analyses will be performed using intent-to-treat analytic strategies. The mixed effect model will be used, which is compatible with unbalanced outcome measurements. The change of SCFA from baseline will be considered as the outcome variable of the mixed model. All time points will be included for the analysis. Covariates including age, sex, BMI and time (a continuous variable) will be adjusted when necessary. In addition, the time and treatment interaction term will be assessed by the likelihood ratio test. The random intercept will be used and the AR1 and/or compound symmetry covariance structure will be considered (and then the likelihood test can help to determine the more appropriate covariance structure). The final model selection will be performed based on information criteria such as Akaike information criterion (AIC) or Bayesian information criterion (BIC). Power: with a sample size of 40 subjects in the treatment arm and 20 subjects in the placebo arm and attrition rate of 5% at day six and 20% at day 30, we would have power of 82% to detect a moderate effect size of Cohen's $d = 0.63$ (assuming the intra-correlation correlation coefficient is 0.3). The α level of 0.05 will be used for the analysis. Since the effect size of previous study (reduction in acetate levels) is Cohen's $d = 1.23$, we should have ample power to detect the treatment effect. (The power calculation is based on the R software and packages simr, sjstats, and pwr).

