The probiotic-supplemented yogurt is composed of the investigational agent, BB-12, and contains the yogurt starter culture YF-L702 (a mixed culture of *Streptococcus thermophilus* and *Lactobacillus delbrueckii* subsp. *bulgaricus*). The yogurt starter culture will be present and alive in the control yogurt. Participants are to provide informed consent at Baseline and complete a 30-day run-in period, during which they will refrain from all probiotics, and begin the antibiotic and yogurt interventions on Day 1.

Participants will be randomized to receive BB-12-supplemented yogurt or control yogurt (without BB-12), in a 2:1 (40:20 participants) allocation (**Figure 1**).

Group 1 (n=40): Probiotic, BB-12-supplemented yogurt, 4-ounces (which delivers $\geq 10^{10}$ CFU of BB-12) taken orally for 14 days and amoxicillin-clavulanate 875/125 mg, twice daily, for 7 days.

Group 2 (n=20): Control yogurt, 4-ounces taken orally for 14 days and amoxicillin-clavulanate 875/125 mg, twice daily, for 7 days.

Figure 1.

Fecal samples will be collected at home (at baseline (pre and post run-in), days 7, 14, 21 and 30) for SCFA and microbiome testing. Participants will be given detailed, written and illustrated instructions on proper sample collection procedures, and research staff will review these protocols with participants during enrollment.

Follow-up phone visits will be completed on Days 7, 14, and 30. Participants will keep a daily diary to track number, shape and consistency of bowel movements, if/when antibiotic and/or yogurt was consumed, Bristol Stool chart, general health, use of other medicines or products, adverse events, and the Gastrointestinal Symptom Rating Scale (GSRS) - Irritable Bowel Syndrome (IBS) version..

Duration: Each participant will be in the study for approximately 8 weeks total. During the first 30 days, the participant will refrain from antibiotics and probiotics (run-in period) and provide two baseline samples. The participant will be taking the antibiotic intervention for 7 days and taking the yogurt intervention for 14 days. There are two more data collection visits on day 21 and 30.

Pre run-in Baseline	Run-in (30 days)	Post run-in Day 0	Day 1	Day 7	Day 14	Day 21	Day 30
Informed Consent	No antibiotics	Fecal sample	AMC start	AMC end	Yogurt end	Fecal sample	Fecal sample
Inclusion/exclusion	No probiotics	Post-run in inclusion/exclusion	Yogurt start	GSRS-IBS	Diary end		

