6. STUDY PROCEDURES

6.1 Schedule of Evaluations

All interventions will be completed by day 14 of the trial. At day 30, participants will provide the final sample and be queried for changes in baseline health and other adverse events.

Table 8. Participant Timeline and Sample/Data Collection Schedule (N=60)

Assessment	Pre-screen	Pre Run-In Baseline	30-day Run-In	Post Run-In (0/+2)	1	7 (±2)	14 (±2)	21 (±2)	30 (±2)
Pre-Screening	X								
Informed Consent Form & Process		X							
Inclusion/Exclusion Criteria		X		X					
Enrollment		X ^a							
Baseline Health Status		X							
Demographic Information		X							
Fecal Microbiome Collection ^a	X		X		X	X	X	X	X
Automated Self-Administered 24-Hour (ASA24®) Dietary Assessment Tool (2 days)			X						
Run-in Period (30 days)			→	→					
Post Run-In Health Status				X					
Randomization			X						
Amoxicillin-clavulanate Intervention (7 days)					→	→			
Yogurt Intervention (14 days)					→	→	→		
Follow-up Data Collection						X	X		X
Daily Assessment Diary ^b (14 days)					→	→	→		
Gastrointestinal Symptom Rating Scale (GSRS-IBS)					X	X	X		
SCFA Testing	X					X			X
16S rRNA Gene Sequences				X		X	X	X	X
Adverse Event Reporting		→		→	→	→	→	→	→

^aEnrollment will occur a minimum of 30 days prior to starting the interventions. Participants will provide one stool sample before the run-in period, refrain from antibiotics and probiotics during this period and provide 1 baseline sample after the run-in period.

^bDiary from days 1-14; information on yogurt consumption/dose, sample number, shape and consistency, health, use of interventions, quality of life and adverse events.

X: collected on day; | → : starting from day; → |: through end day

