6.5.2 Baseline Assessments

Once informed consent is given and it is confirmed that the participant meets all inclusion and exclusion criteria, baseline data will be collected. These include: Baseline Health Status and Demographic Information.

Stools will be collected multiple times throughout the study. Research staff will be trained on how to properly transport stool and how to instruct participants on collecting stool.

During the initial visit, participants will also be given all materials to collect stools, the diary, and study materials as well as the initial compensation. The participant will commence the 30-day run-in period. During this 30-day run-in period, the participant will refrain from antibiotics and probiotics (a "What Not to Eat list will be provided) and provide two baseline stool samples--one pre run-in, and one post run-in (prior to starting the yogurt and antibiotics).

Additionally, the research staff will phone the participant two times during the run-in period to collect 24-hour diet recall data. The instrument, the Automated Self-Administered 24-Hour (ASA24®) Dietary Assessment Tool, will be administered by the research staff and recorded for one weekday and one weekend day (<https://epi.grants.cancer.gov/asa24/>).

Following the run-in period and prior to the yogurt start day (day 1), research staff will contact the participant in order to complete the Post Run-in Health Status form and repeat the Inclusion/Exclusion form to ensure that the participants are still eligible. Participants who start an exclusionary medication or experience an onset of an exclusionary, nontransient health condition from the time of enrollment will be withdrawn from the study.

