Should the participant take any antibiotics during this 30-day run-in period, they will start another 30-day run-in cycle after the antibiotics are completed. The initiation of the yogurt and antibiotic interventions (day 1) will be delayed until this additional run-in cycle is complete. Participants who take any non-study probiotics during this 30-day run-in period will document any use on the Post Run-In Health Status form. Participants who need to delay their day 1 (initiation of the yogurt and antibiotic intervention), e.g. to complete a full 30-day run-in or due to transient conditions, can be held for a future cohort for up to 90 days from the day the informed consent was signed, without the need to re-consent. After 90 days, the participant will be re-consented prior to starting the interventions.

Participants who are still eligible based on the completion of the Post Run-in Health Status and post run-in Inclusion/Exclusion forms will then be randomized to receive the BB-12 yogurt or control yogurt for days 1 through 14 to be taken once a day. In addition, they will also receive measuring cups that denote a level of 4 ounces. The amount of BB-12 supplemented yogurt drink to be supplied will be 4 ounces per day, which is slightly more than 100 grams/day.

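### The primary outcome is change in SCFA from baseline, but two pre-treatment stools are called baseline, neither is chosen, and Table 8 marks only one pre-treatment SCFA test

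*Combined protocol and SAP*

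**What the plan says.** - **Outcome.** Section 9.7: "The change of SCFA from baseline will be considered as the outcome variable of the mixed model". Section 9.1 compares days 7 and 30 with the baseline values, Section 9.5.1 takes the day 7 difference in antibiotic-induced change, and Section 9.8 plans to impute a missing baseline outcome. None says which stool supplies the baseline.
- **Two stools share the name.** Section 6.5.2 has participants "provide two baseline stool samples--one pre run-in, and one post run-in".
- **The name moves.** In the Précis it is the consent visit: "Participants are to provide informed consent at Baseline and complete a 30-day run-in period". The Précis timeline calls the post run-in visit Day 0. Footnote a to Table 8 speaks of one stool before the run-in and then has participants "provide 1 baseline sample after the run-in period".
- **Planned assays.** Précis: "Fecal samples will be collected at home (at baseline (pre and post run-in), days 7, 14, 21 and 30) for SCFA and microbiome testing". Section 3 likewise allots one tube to SCFA and one to the microbiome, and lists both pre-treatment collections.
- **Table 8, as extracted.** The SCFA row has one pre-treatment mark, then days 7 and 30. The row "16S rRNA Gene Sequences" has one pre-treatment mark, then days 7, 14, 21 and 30.
- **Timing.** Section 4.5 puts consent about 45-60 days before the interventions. Section 6.5.2 says delayed participants "can be held for a future cohort for up to 90 days from the day the informed consent was signed" without re-consent.

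**The concern.** The two stools are not interchangeable. The first precedes the wash-out, and Section 4.4 does not exclude recent antibiotic or probiotic use, so that stool may reflect either. The second is taken after at least 30 days without them, just before the first dose.

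The primary hypothesis contains two within-person claims: antibiotics lower SCFA, and SCFA returns to baseline. Everyone receives the antibiotic, so no untreated group shows how far acetate moves by itself. If Table 8 were followed and its single SCFA test fell before the run-in, acetate would never be measured after the wash-out and before treatment. Both claims would then mix the antibiotic effect with whatever happened during the run-in. If both stools are assayed but no rule is written, the baseline can be picked after the data are seen.

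**Working it through.** **1. How old the first stool is.** Footnote a places it before a run-in of at least 30 days, so it is at least about 30 days old at day 1. The 45-60 days in Section 4.5 and the 90-day limit in Section 6.5.2 run from consent, not from the stool. They show only that it can be older. After an antibiotic in the run-in, the 30 days are repeated (Sections 5.3.1 and 6.5.2). Whether the first stool is recollected is not stated.

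**2. What anchoring on it does.** Let D be a participant's drift from the pre to the post run-in stool. Then change from pre = change from post + D. Within an arm, the mean change moves by the mean of D, which is not antibiotic effect. Between arms, D arises before randomisation (Sections 6.5.2 and 6.5.3), so its expected mean is equal in both arms and cancels. The documents give no size for D.

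**3. The plan's own power figure.** Sections 9.2 and 9.7 give 82% at d = 0.63, 40:20, correlation r = 0.3, losses of 5% (day six) and 20% (day 30), alpha 0.05. Assumptions: two-sided test, unit variance, equal correlation, a constant effect over days 7 and 30, and one baseline as covariate.

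- Residual variance 1 - 0.09 = 0.91; covariance 0.3 - 0.09 = 0.21.
- Information per participant: 0.80 × 2/(0.91 + 0.21) + 0.15/0.91 = 1.593.
- SE = √[(1/20 + 1/40)/1.593] = 0.217.
- Power = Φ(0.63/0.217 - 1.96) = 82.7%, which reproduces the stated 82%.

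**4. What the second stool adds at r = 0.3, equal correlation.**

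- Change from one stool: 2(1 - r) = 1.40.
- Change from the mean of two: 1 + (1 + r)/2 - 2r = 1.5(1 - r) = 1.05.
- One covariate: 1 - r² = 0.910.
- Both as covariates: 1 - 2r²/(1 + r) = 0.862, which is 5% less.

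Approximate power by the method of step 3, with d on the raw SD:

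| Model | One stool | Both stools |
|---|---|---|
| Change score (both = mean) | 57.3% | 74.2% |
| Baseline as covariate | 82.7% | 85.8% |

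**5. AR1, which Section 9.7 also considers.** With correlation r between successive stools and r² between the first stool and day 7, the change from the mean of two has variance 1.5 - 0.5r - r².

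| r | Post run-in alone, 2(1 - r) | Mean of two | Pre run-in alone, 2(1 - r²) |
|---|---|---|---|
| 0.3 | 1.40 | 1.26 | 1.82 |
| 0.5 | 1.00 | 1.00 | 1.50 |
| 0.7 | 0.60 | 0.66 | 1.02 |

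Against the post run-in stool alone, averaging gains 10%, gains nothing, and loses 10%. Anchoring on the pre run-in stool alone costs 30% to 70% in variance here, and nothing under equal correlation. As an extra covariate, the older stool adds nothing under AR1, because day 7 depends on it only through the later stool, but apart from one degree of freedom it does no harm.

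**The case against.** **Table 8 is damaged.** In the extracted text the SCFA mark falls under Pre-screen, before consent. Randomization falls under the run-in, although Section 6.5.3 places it afterwards. The fecal row has seven marks, one of them on day 1, for six planned stools (Section 6.2.3). Neither columns nor counts can be trusted. This stands. A reader might infer that acetate and 16S are anchored to different days, but the documents cannot establish it. The table is a query, not a finding.

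**The second stool is not shown to be wasted.** The Précis sends both stools for testing, and Section 9.7 includes all time points. This stands too. What can be said is that the use of the second stool is unspecified.

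**The primary test is not biased.** A reader might infer that a poor anchor distorts the BB-12 comparison. It does not, for the reason in step 2 of the working.

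**The precision gain is fragile.** The 25% fall in change variance from averaging needs equal correlation, and most of the power difference comes from using a change score rather than a covariate, which is a separate matter. This stands. Nor does 57.3% show that the trial is underpowered: the documents do not give the simulation model, and d may have been scaled to the SD of the change.

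None of this supplies the missing definition or reconciles Table 8 with the Précis and Section 3.

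**Conclusion.** The point holds as a gap in definition, with a conflict in the schedule to be resolved. The primary outcome has no named anchor. If SCFA were run only on the pre run-in stool, the within-arm antibiotic effect and the return to baseline would include wash-out drift and any interim antibiotic, by an amount the documents do not allow one to estimate. The between-arm comparison would remain unbiased, with lower precision to the extent that the older stool is less correlated with day 7.

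The gain from using both stools is modest: about 5% in residual variance as covariates at r = 0.3 under equal correlation, and none under AR1. The case for change therefore rests mainly on interpretation and on fixing the baseline before the data are seen. It merits correction because it is cheap and the stools are already to be collected.

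**What to change.** 1. State in Sections 9.1, 9.5 and 9.7 that baseline for SCFA and 16S is the post run-in stool taken before the first dose.
2. Align Table 8 with the Précis and Section 3, so that SCFA and 16S are run on both pre-treatment stools. Check the marks against the source table.
3. Enter the pre run-in value as an additional baseline covariate and do not average it into the anchor. The post run-in value must be a covariate as well: under equal correlation, Cov(Y - post, pre) = r - r = 0, so the pre run-in value alone adds nothing to a change-score model. Section 9.7 names age, sex, BMI and time as covariates, but not baseline SCFA.
4. State the rule for a missing stool and for a restarted run-in, including whether the first stool is recollected and which values enter the imputation in Section 9.8.
5. Report the pre-to-post run-in change in acetate and in Bray-Curtis as a descriptive reference for drift without study treatment, noting that it includes probiotic withdrawal.

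Cost: protocol wording and, if Table 8 reflects current intent, one more SCFA assay and one more 16S library for each of 60 participants, at most about 60 of each. If the Précis reflects current intent, there is no extra assay. No further stools are needed.

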1. STUDY OBJECTIVES

1.1 Primary Objective

To determine the ability of BB-12 to impact antibiotic-induced reduction in SCFA concentration as reflected by the levels of acetate on day 7. SCFA produced by anaerobic gut microbiota will be quantified from human fecal samples via liquid chromatography-tandem mass spectrometry (LC-MS/MS).

Primary Hypothesis: Antibiotics will result in a reduction in fecal SCFA by day 7. BB-12 supplementation will protect against antibiotic-induced SCFA reduction and/or be associated with a quicker return to baseline SCFA levels, as compared to the control group.

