3.1 Primary Outcome Measure

The primary outcome is to determine the ability of BB-12 to impact antibiotic-induced reduction in SCFA as reflected by the levels of acetate on day 7, the most abundant primary colonic SCFA. SCFA produced by anaerobic gut microbiota will be quantified from human fecal samples via liquid chromatography-tandem mass spectrometry (LC-MS/MS).

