9.3 Definition of Populations

Statistical analysis on the primary outcome will be performed using the intention to treat principle; all subjects enrolled and randomized will be accounted for in the final analysis in their randomized group.

We will also examine the per protocol group separately and report both the intention-to-treat and per protocol analyses. The mixed effect model will be used, which is compatible with unbalanced outcome measurements. The multiple imputation analysis will be performed when the covariates are missing.

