9.5 Outcomes

9.5.1 Primary Outcome

The primary outcome is a difference, measured at day 7, in antibiotic-induced changes in fecal SCFA (with a particular focus on acetate) in participants receiving BB-12-supplemented yogurt versus non-supplemented control yogurt.

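### The primary outcome is the day-7 acetate difference, but the Section 9.7 mixed model names no day-7 contrast and leaves the treatment-by-time term to be settled from the data

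*Combined protocol and SAP*

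**What the plan says.** **The outcome.** Section 9.5.1: "The primary outcome is a difference, measured at day 7, in antibiotic-induced changes in fecal SCFA". Section 3.1 puts the same outcome "as reflected by the levels of acetate on day 7". The hypothesis in Section 1.1 is wider: it expects protection against the fall "and/or be associated with a quicker return to baseline SCFA levels".

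**The model.** Section 9.7 analyses change from baseline in a mixed model with a random intercept. "All time points will be included for the analysis". "Covariates including age, sex, BMI and time (a continuous variable) will be adjusted when necessary". It adds that "the time and treatment interaction term will be assessed by the likelihood ratio test", without saying what is reported if the term is kept or dropped. Final model selection is by AIC or BIC. Day 7 is not mentioned in Section 9.7. Section 9.3 also points to this model: "The mixed effect model will be used, which is compatible with unbalanced outcome measurements".

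**The other method.** Section 9.1 compares mean acetate at days 7 and 30 with baseline by one-way ANOVA with a post hoc test. A significant difference during or after the antibiotic would count as support for the hypothesis and for moving to R33. Section 9.1 also computes Cohen's d at each of days 7 and 30 as the R33 milestone, met if either reaches 0.6. No section ranks the ANOVA against the mixed model as the test of the day-7 outcome.

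**The visits.** The SCFA row of Table 8 (as extracted), Section 9.1 and the attrition figures in Section 9.2 point to two post-baseline SCFA visits, days 7 and 30. The Précis has samples collected for SCFA at days 7, 14, 21 and 30. There are two baseline samples, before and after the run-in, and Section 9.7 does not say which is the baseline.

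**The concern.** Two analysts could follow Section 9.7 faithfully and report different quantities as the primary result. One keeps the interaction and reads off day 7. The other drops it and reports one treatment effect averaged over visits.

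The two agree only if the arm difference is the same at every visit, and the protocol gives reasons to doubt that. Section 9.1 expects acetate to return toward baseline once the antibiotic stops, and Section 1.1 allows the benefit to be faster recovery. An effect that fades dilutes the averaged term. An effect that appears only later can make the averaged term significant with nothing at day 7. In both cases the 0.05 level is attached to something other than the stated outcome, and the data decide which quantity that is.

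**Working it through.** **Inputs from Section 9.2.** Acetate 45 (SD 16) falling to 24 (SD 18) umol/g; expected falls of 42% (control) and at most 15% (BB-12); 40:20 allocation; attrition 5% at day six and 20% at day 30; correlation 0.3; alpha 0.05.

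**Assumptions.** Two-sided test; SCFA visits at days 7 and 30; the day-six attrition applied at day 7, giving 38/19 then 32/16 observed; monotone dropout; known covariance; normal approximation. How the effect evolves after day 7 is not in the documents, so it is varied.

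**1. The plan's own figures.**
- Pooled SD = √((16² + 18²)/2) = 17.03. Earlier-study effect = 21/17.03 = 1.23, as stated.
- The stated 82% at d = 0.63 cannot be traced to a model, because Section 9.2 does not name the visits or model simulated. Averaging days 7 and 30 with the stated attrition gives SE 0.233 and 77% on levels, and SE 0.217 and 83% baseline-adjusted. On levels without attrition it gives 81%.

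**2. Day-7 contrast, change scores.**
- Difference = 45 × (0.42 − 0.15) = 12.15 umol/g.
- SD of change = 17.03 × √(2 × (1 − 0.3)) = 20.15.
- SE = 20.15 × √(1/38 + 1/19) = 5.66.
- Power = Φ(12.15/5.66 − 1.96) = Φ(0.19) = 57%, whatever happens by day 30.
- Baseline-adjusted: SD = 17.03 × √(1 − 0.3²) = 16.24, SE 4.56, power 76%.

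**3. Treatment term without interaction, change scores.** Generalised least squares, with covariance (1 − 0.3) × 17.03² between the two changes, gives day 7 a weight of 0.561 and SE 5.00. If a fraction f of the effect remains at day 30, the estimate is 12.15 × (0.561 + 0.439f).

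| Effect left at day 30 | Averaged estimate | Power | Day-7 contrast | Power |
|---|---|---|---|---|
| None | 6.8 | 28% | 12.15 | 57% |
| Half | 9.5 | 47% | 12.15 | 57% |
| All | 12.15 | 68% | 12.15 | 57% |

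If the effect is gone by day 30, the averaged estimate is 6.6 to 6.9 on change, level or baseline-adjusted scales for correlations 0.1 to 0.7. In the reverse case (levels, no effect at day 7, d = 0.63 at day 30), the averaged term is significant in 23% of trials.

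**4. How often the interaction is kept.** The SE of the day-7 minus day-30 difference is 6.05, so the expected z is 12.15/6.05 = 2.01 (effect gone), 1.00 (half left) and 0.50 (three quarters left). The term is kept when z² exceeds the selector's threshold.

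| Selector | Threshold | Gone | Half left | Three quarters left |
|---|---|---|---|---|
| Likelihood ratio test at 5% | 3.84 | 52% | 17% | 8% |
| AIC | 2 | 72% | 35% | 21% |
| BIC (log of 60 subjects to log of 105 observations) | 4.09–4.65 | 44–49% | 13–16% | 5–7% |

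**5. Day-7 power at the plan's d = 0.63, 38:19.** Levels: SE 0.281, 61%. Baseline-adjusted: SE 0.268, 65%. Unadjusted change, with d scaled to the level SD: SE 0.332, 47%. These differ from step 2 because 12.15/17.03 is d = 0.71.

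**The case against.** The strongest reply is that the plan can already deliver the day-7 result. With two SCFA visits, a model with straight-line time and its interaction with treatment recovers the day-7 difference exactly. Section 9.1 also guarantees a day-7 Cohen's d. This stands, and it rules out the reading that Section 9.7 simply pools all visits: averaging occurs only if the interaction is left out. It does not meet the point, because keeping the interaction is optional, its day-7 value is not named as the primary test, and Cohen's d serves as a milestone that day 30 can also satisfy.

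A second reply is that the hypothesis includes recovery, so a longitudinal analysis is apt, and averaging has more power if the effect lasts. Both parts are right. At correlation 0.3, averaging overtakes the day-7 contrast once a fraction between 0.575 and 0.735 of the difference persists, depending on the scale. That could be a reason to choose a different primary outcome, but Section 9.5.1 has chosen day 7.

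Third, the AIC/BIC sentence follows the one on covariance structure and may not be meant for fixed effects, and no threshold is given for the likelihood ratio test. That is fair. No single retention rate can therefore be called the plan's, and a reader should not infer from the 5% column alone that the interaction will usually be lost. AIC would keep it in 72% of trials if the effect were gone by day 30.

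Finally, a reader might infer that the ANOVA has no role. Section 9.1 gives it one, support for the hypothesis and for R33. Only its rank against the mixed model is missing.

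**Conclusion.** The concern holds as a gap between the stated outcome and the specified test. Day 7 is fixed as primary, yet Section 9.7 names no day-7 contrast, does not require the interaction, and leaves the choice to a selector it does not fully state. The standing of the ANOVA relative to the mixed model is also open.

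The gap follows from the text and needs no calculation. Its size is conditional. Under the inputs above, the reported effect could be 6.8 rather than 12.15 umol/g, with 28% rather than 57% power, if the effect has gone by day 30. There is no bias, and averaging gains power, if the effect is constant. The documents do not say which will happen.

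A reader might also infer that the stated 82% power is wrong. The documents do not show that: a baseline-adjusted average over days 7 and 30 with the stated attrition gives about 83%. What can be said is that 82% is not the power of a day-7 comparison at d = 0.63, which is 47% to 65% depending on the scale.

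**What to change.** **Section 9.7.** Make the primary test the day-7 treatment contrast from a model that always contains categorical visit and treatment-by-visit. Adjust for baseline acetate from a named sample (before or after the run-in). Fix the covariates and covariance structure in advance, and use no likelihood-ratio, AIC or BIC selection for this test. Report day 30 as a secondary contrast for recovery. List the SCFA visits that enter the model. This matters because, if days 14 and 21 were also assayed, straight-line time would no longer recover day 7: for an effect present at day 7 only, it would return 8.4 instead of 12.15.

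**Section 9.1.** State that the ANOVA and the day-7 and day-30 Cohen's d are supportive or R33 go/no-go criteria and are not the primary test.

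**Section 9.2, and its repeat in 9.7.** Give the power of the day-7 contrast on the chosen scale, and say which visits and model the 82% describes.

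**Cost.** Wording only, with no new data. If the effect is constant to day 30, the day-7 test has less power than averaging: 57% against 68% on change scores, 76% against 91% baseline-adjusted. The power stated for the primary test would also be lower than 82%.
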